#### 6.6.3.1. Dose Reductions, Interruptions, and Delays

A dose reduction is defined as a nonzero dose that is less than the planned and previous non-zero dose. The planned dose is the same as the prior dose except for C1D4 and C1D8.

The number and percentage of participants with at least 1 dose reduction as well as a breakdown of dose reductions  $(1/2/3/ \ge 4)$  will be summarized by cohort. In addition, the number and percentage of participants with at least 1 dose reduction due to AE will also be summarized.

An interruption is defined as a continuous missed scheduled dose based on the planned dosing frequency (QW or Q2W). The number and percentage of participants with dose interruptions as well as a breakdown of dose interruptions  $(1/2/3/\geq 4)$  will be summarized by cohort and overall. In addition, the number and percentage of participants with at least 1 dose interruption due to AE will also be summarized. Percentages will be calculated based on the total number of participants in the Safety Analysis Set.

A dose delay will be derived based on study drug administration date and will be grouped into the following categories based on the deviation of the actual to the planned treatment administration day (relative to the previous treatment administration date):

- No delay;
- 1-3 days delay;
- 4-6 days delay;
- 7 or more days delay (only in the Q2W schedule).

The number and percentage of participants with delayed study drug administration and maximum length of delay, ie, the worst case of delay if participants have multiple dose delays will be summarized by cohort, as applicable.

# 6.6.4. Concomitant Medications and Nondrug Treatments

The following analyses will be based on the Safety Analysis Set and will be summarized by cohort.

**Concomitant medications** are medications, other than study medications, which started prior to first dose date of study intervention and continued on during the on-treatment period as well as those started during the on-treatment period. **Prior medications** are medications, other than study medications, which are started before the first dose of study intervention.

Prior and concomitant medications will be summarized from the 'General Concomitant Medications' eCRF page. **Pre-medications** required for CRS will also be summarized (for C1D1, C1D4, C1D8, and other) separately from the 'Concomitant Medications – Pre-Medications (PREMED)' eCRF page.

Summary of prior medication and summary of concomitant medications (excluding for CRS prophylaxis) will include the number and percentage of participants by Anatomical Therapeutic Chemical (ATC) Classification Level 2 and PT. A participant will be counted only once within a given drug class and within a given drug name, even if he or she received the same medication at different times. If any prior or concomitant medication is classified into multiple ATC classes, the medication will be summarized separately under each of these ATC classes. The summary tables will be sorted by alphabetical ATC class and descending frequency of drug name in a given ATC class by Cohort A. Medications without an ATC classification Level 2 coded term will be summarized under the 'Unavailable ATC classification' category.

Summary of prior and concomitant medications for CRS prophylaxis will include the number and percentage of participants by PT only.

#### 6.6.5. Subsequent Anticancer Therapies

The following analyses will be based on the Safety Analysis Set and will be summarized by cohort.

Number and percentage of participants with any anticancer therapy after discontinuation of study intervention will be tabulated overall and by type of therapy based on the data collected from the 'Next Anticancer Therapy (NXT CNCR)' eCRF pages, 'Non-drug Treatments (NXT RAD)', 'Non-drug Treatments (NXT SURG)', and 'Transplant details (TRANSPLT)' eCRF pages.

Subsequent anticancer drug treatment will be summarized by PT.

#### 6.7. Safety Summaries and Analyses

The Safety Analysis Set will be the primary population for safety evaluations. Summaries of AEs and other safety parameters will be based on the Safety Analysis Set by cohort and overall.

#### 6.7.1. Adverse Events

All analyses will be based on treatment emergent adverse events (TEAEs) unless otherwise specified. Treatment emergent is defined in Section 3.5. AEs not considered treatment emergent will be flagged in data listings. Summaries of TEAEs due to COVID-19 may be produced if appropriate.

A high-level summary of adverse events (all causality and treatment-related, separately) will include the number and percent of participants with:

- Any TEAEs;
- Serious TEAEs;
- Grade 3-4 TEAEs;
- Grade 5 TEAEs;
- TEAEs leading to dose interruptions;
- TEAEs leading to dose reductions;
- TEAEs leading to dose interruptions or reductions;
- TEAEs leading to permanent discontinuation of study intervention;
- CRS;

- ICANS;
- Peripheral neuropathy.

Seriousness, toxicity grade, and withdrawal from drug are as reported by the investigator on the adverse event CRF.

An event will be considered treatment-related if the investigator considered the event as related to the study drug or if relationship is missing.

For all the AE summaries by SOC and PT, or PT only, the following cytopenias will be clustered. Each participant will be counted only once within each SOC and clustered terms. However, the number of total events will be based on the individual PTs.

- Thrombocytopenia (PT=Thrombocytopenia; Platelet count decreased);
- Anaemia (PT=Anaemia; Haemoglobin decreased, Red blood cell count decreased, Haematocrit decreased, Normochromic anaemia, Normocytic anaemia, Normochromic normocytic anaemia);
- Neutropenia (PT=Neutropenia; Neutrophil count decreased, Neutrophil percentage decreased, Cyclic neutropenia, Agranulocytosis, Granulocytopenia, Granulocyte count decreased);
- Leukopenia (PT=Leukopenia; White blood cell count decreased);
- Lymphopenia (PT=Lymphopenia; Lymphocyte count decreased, Lymphocyte percentage decreased, CD4 lymphocytes decreased, CD4 lymphocyte percentage decreased, CD8 lymphocytes decreased, CD8 lymphocyte percentage decreased).

Summaries by SOC and PT by alphabetical order for SOC and by descending order of frequency for PT in two cohorts combined will be provided for:

- TEAEs (all causality and treatment-related);
- TEAEs by maximum severity grade (all causality and treatment-related);
- TEAEs with Grade 3-4 (all causality and treatment-related);
- TEAEs leading to death (all causality and treatment-related);
- TEAEs leading to dose interruptions (all causality);
- TEAEs leading to dose reductions (all causality);
- TEAEs leading to dose interruptions or reductions (all causality);

- TEAEs leading to permanent discontinuation of study medication (all causality and treatment-related);
- TEAEs by maximum severity grade before and after the switch to Q2W (all causality);
- Serious TEAEs (all causality and treatment-related).

The following summaries will be provided by PT only (ie, summaries will not include SOC) in descending order of the overall frequency in two cohorts combined:

- Most common TEAEs in either cohort (all causality and treatment-related, separately) by PT and maximum severity grade;
- Most common serious TEAEs in either cohort (all causality) by PT and maximum severity grade.

Each participant will be counted only once within each SOC and PT.

In case a participant has events with missing and non-missing severity grades, the maximum of the non-missing grade will be displayed. Missing grade will only be displayed if an event has been reported only once for a participant and the grade is missing.

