6.6.3. Dose Modification Based on Durable Overall Response

If a participant has received QW dosing for at least 6 cycles and has achieved an IMWG response category of PR or better persisting for at least 2 months, the dose interval will be changed from QW to Q2W (eg, beginning C7D1).

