9.2. Sample Size Determination

The sample size for Cohort A and Cohort B was calculated to provide adequate power for testing the statistical hypotheses regarding the primary endpoint of ORR independently in the two cohorts using a two-stage design based on the exact binomial distribution. A total of 120 participants enrolled and treated in Cohort A provides approximately 98% power to reject the null hypothesis (ORR by BICR of 30%) when the alternative hypothesis that ORR by BICR of 48% is true, with a 1-sided significance level of 0.025. Similarly, a total of 60 participants enrolled and treated in Cohort B provides approximately 95% power to reject the null hypothesis (ORR by BICR of 15%) when the alternative hypothesis that ORR by BICR of 34% is true, with a 1-sided significance level of 0.025.

An IA for both (non-binding) futility and efficacy will be conducted for Cohort A and Cohort B; details are described in Section 9.5.

At the time of the SAP amendment prior to the interim analysis, enrollment had exceeded the 120 Cohort A and 60 Cohort B participants. Enrollment closed in January 2022 with 123 Cohort A and 64 Cohort B participants enrolled and treated.

At the time of the final analysis, the rule for rejecting the null hypothesis based on an exact binomial test will depend on the number of participants enrolled and treated in each cohort, respectively. At the final analysis in Cohort A, if there are ≥ 48 (39.0%) objective responders by BICR observed out of 123 participants enrolled and treated in the cohort, it will be concluded that the null hypothesis is rejected, and the cohort has demonstrated that the true

ORR by BICR exceeds 30%. At the final analysis in Cohort B, if there are ≥ 16 (25.0%) objective responders by BICR observed out of 64 participants enrolled and treated in the cohort, it will be concluded that the null hypothesis is rejected, and the cohort has demonstrated that the true ORR by BICR exceeds 15%.

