## 4. ANALYSIS SETS (POPULATIONS FOR ANALYSIS)

For purposes of analysis, the following analysis sets are defined:

Defined Analysis Set	Description
Safety Analysis Set	The safety analysis set in each cohort will include all enrolled participants in the respective cohort who received at least one dose of study intervention. This will be the primary analysis population for evaluating participant characteristics, treatment administration/compliance and safety endpoints.
Final Analysis Evaluable Set	The final analysis evaluable set in each cohort will include all enrolled participants in the respective cohort who received at least one dose of study intervention. This will be the primary analysis population for evaluating efficacy endpoints. This is the same as the safety analysis set thus only the "safety analysis set" terminology will be used.
Interim Analysis Evaluable Set A	The interim analysis evaluable analysis set A will include the first 90 enrolled participants who received at least one dose of study intervention in Cohort A. This will be the primary analysis population for evaluating efficacy endpoints at the interim analysis for Cohort A.

Interim Analysis Evaluable Set B	The interim analysis evaluable analysis set B will include the first 30 enrolled participants who received at least one dose of study intervention in Cohort B. This will be the primary analysis population for evaluating efficacy endpoints at the interim analysis for Cohort B.
PK Analysis Set	The PK analysis set is a subset of the safety analysis set and will include participants who have at least one postdose concentration measurement.
Immunogenicity Analysis Set	The immunogenicity analysis set is a subset of the safety analysis set and will include participants who have at least one sample tested for ADA.
Biomarker Analysis Set	The biomarker parameter analysis set in each cohort is a subset of the safety analysis set and will include participants who have at least one baseline biomarker assessment.
	Analysis sets will be defined separately for biomarkers based on blood, saliva, and bone marrow samples.
PRO Analysis Set	The PRO analysis set in each cohort will include all participants in the safety analysis set who completed a baseline (last PRO assessment prior to or on the first dose of study intervention) and at least one post-baseline PRO assessment.

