### 5.2.5. Definition of Cycle and Cycle Day

Cycle start and end dates are derived per participant. The definition for each cycle is driven by study drug elranatamab. Elranatamab is administered on Days 1, 8, 15 and 22 of each 28-day cycle. As described in Protocol Section 6.1.1, if a participant has received QW dosing for at least 6 cycles and has achieved an IMWG response category of PR or better persisting for at least 2 months, the dosing interval will be changed from QW to Q2W. If the participant subsequently begins to have an increase of disease burden not yet qualifying as PD according to IMWG criteria, dose intervals should return to weekly dosing. If the dose interval is changed, cycles should remain the same length (ie, 4-week cycles). In either dosing scenario, the nominal cycle length is 28 days.

- For Cycle 1, the actual cycle starts date is the date each participant receives the first non-zero study intervention;
- For all other cycles, the actual cycle start date for each participant is the earliest start date of dosing in the Cycle X Day 1 visit CRF exposure page;
- For all but the last cycle;
  - Actual cycle stop date is calculated as the start date of the next cycle minus 1 day;
  - Actual cycle duration is calculated from Day 1 of a cycle to the day prior to Day 1 of the next cycle, as follows:

Actual Cycle Duration (weeks) = (cycle stop date – cycle start date + 1)/7

• For the last cycle, actual cycle duration is based on the actual cycle stop date which is last zero/non-zero dose date + (7 days if on QW or 14 days if on Q2W) – 1 day. If C1D4 is the last visit, cycle stop date is Day 7 if C1D4 occurred by then.

The cycle day will be calculated as:

Cycle day = Date of the assessment/event – cycle start date + 1.

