#### 6.6.3. Study Intervention Exposure

Exposure will be summarized based on the Safety Analysis Set.

Elranatamab is administered as a subcutaneous injection at 76 mg once every week on Days 1, 8, 15 and 21 of each 28-day cycle. Elranatamab is also administered on C1D4. A minimum of 2 days should be maintained between the 2 step-up priming doses (C1D1 and C1D4) and a minimum of 3 days between C1D4 dose and the first full dose (C1D8); a minimum of 6 days should be maintained between doses thereafter. The dose of elranatamab should be increased to 76 mg on C1D8 as long as the participant meets the criteria listed in Protocol Section 6.6.1. If a participant does not meet these criteria on C1D8, initiation of dosing with 76 mg should be deferred until the criteria are met. In addition, if a participant has received QW dosing for at least 6 cycles and has achieved an IMWG response category of PR or better persisting for at least 2 months, the dose interval will be changed from QW to Q2W. If the participant subsequently begins to have an increase of disease burden not yet qualifying as PD according to IMWG criteria, dose intervals should return to weekly dosing. If the dose interval is changed, cycles should remain the same length (ie, 4-week cycles).

The summary of treatment exposure elranatamab will include the following information:

• Treatment duration (months);

- Number of cycles started per participant (mean, median, min, max);
- Number and percent of participants starting a cycle (any cycle, 1, 2, 3, 4, 5, 6, 7, 8, 9, 10, 11, ≥12-<18, ≥18-<24, ≥24 cycles);
- Total cumulative dose (mg);
- Overall dose intensity (mg/week);
- Overall relative dose (%);
- Overall relative dose intensity (%);
- Number and percent of participants who received 44 mg on the C1D1 visit;
- Number and percent of participants who received 32 mg on the C1D4 visit;
- Number and percent of participants who received 76 mg on the C1D8 visit;
- Number and percent of participants after 6 cycles who switched from QW to Q2W;
- Number and percent of participants, among those switching from QW to Q2W, who switched back to QW.

The treatment duration of elranatamab (in weeks) during the study for a participant is defined as:

Treatment duration (months) = (last dose date – first dose date + 1)/30.4375

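### The planned before/after-Q2W adverse event table has no restriction to switchers, no time at risk and no rule for returns to weekly dosing, so its crude percentages can differ when the interval has no effect

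*SAP*

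**What the plan says.** Among the SOC and preferred-term summaries in SAP 6.7.1 is one line on the dosing interval: "TEAEs by maximum severity grade before and after the switch to Q2W (all causality". No method is attached. The general rule in SAP 6.7 is "Summaries of AEs and other safety parameters will be based on the Safety Analysis Set by cohort and overall", and SAP 4 defines that set as "all enrolled participants in the respective cohort who received at least one dose of study intervention". Protocol 9.2 gives its size: "Enrollment closed in January 2022 with 123 Cohort A and 64 Cohort B participants enrolled and treated", which is 123 + 64 = 187.

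Under Protocol 6.6.3 a participant moves to Q2W who "has received QW dosing for at least 6 cycles and has achieved an IMWG response category of PR or better", with the response lasting at least 2 months. SAP 5.2.5 adds: "In either dosing scenario, the nominal cycle length is 28 days". SAP 5.2.5 and 6.6.3 also foresee that, if disease burden rises without yet meeting PD, "dose intervals should return to weekly dosing". The exposure summaries count this: "Number and percent of participants, among those switching from QW to Q2W, who switched back to QW". No adverse event rule refers to it.

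SAP 6.7.1 counts each participant once within a SOC or preferred term. The on-treatment period in SAP 3.5 runs from first dose to 90 days after last dose, or to the day before new anticancer therapy if that is earlier.

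No other safety summary (events of special or clinical interest, deaths, laboratory data, ECG) is split by interval. The only other before/after item is ORR in SAP 6.1.3.

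**The concern.** Four features make the two columns unlike each other, whatever the interval does.

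- **Population.** Under the default, the table falls on everyone treated, although only switchers can have an event after the switch. The SAP does not say whether someone who never switches belongs in the before column.
- **Time at risk.** A once-per-participant percentage grows with observation time. Switchers have at least six cycles before the switch. The time after it can be any length, plus up to 90 days after the last dose.
- **Priming.** The before period contains the step-up doses, where CRS is mainly expected.
- **Return to QW.** Nothing closes the after period when weekly dosing resumes, so later events would count under Q2W.

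This is the SAP's only safety description of Q2W, a planned part of the regimen for durable responders, and readers will compare its columns. Two programmers could also build it with different denominators and periods.

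**Working it through.** The documents give no rate, target or sample size for this table, so there is no plan figure to reproduce. The check asks how far the columns can drift apart when the interval has no effect.

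**Inputs from the documents**
- Shortest weekly dosing before a switch: 6 × 28 = 168 days. With the SAP 5.2.12 conversion, 168 / 30.4375 = 5.52 months.
- Predicted any-grade CRS after the 12 mg dose on C1D1: 55% (95% CI 29% to 78%), Protocol 4.3.
- One count per participant per SOC or preferred term, SAP 6.7.1.

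**Assumptions (not in the documents)**
- A constant first-event rate, equal in both periods: 0.10 per person-month, range 0.03 to 0.20.
- 2 to 9 months observed after the switch.
- 30% to 70% of participants switch.

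Formula: P(at least one event) = 1 − exp(−rate × months).

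**1. Time at risk alone, switchers only**

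| Rate per month | Before, 5.52 months | After, 2 months | After, 4 months | After, 6 months | After, 9 months |
|---|---|---|---|---|---|
| 0.03 | 15.3% | 5.8% | 11.3% | 16.5% | 23.7% |
| 0.10 | 42.4% | 18.1% | 33.0% | 45.1% | 59.3% |
| 0.20 | 66.8% | 33.0% | 55.1% | 69.9% | 83.5% |

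At every rate the after column starts below the before column and ends above it.

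**2. Priming CRS alone.** Take equal time (5.52 months) in both periods, rate 0.10, and CRS independent of other events. Any TEAE before = 1 − (1 − 0.55) × exp(−0.552) = 74.1%, against 42.4% after. Over the CRS interval of 29% to 78%, the before figure runs from 59.1% to 87.3%.

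**3. Denominator alone.** At 6 months after and rate 0.10, 45.1% of switchers have an event. On the whole Safety Analysis Set this becomes 0.30 × 45.1% = 13.5%, 0.50 × 45.1% = 22.6%, or 0.70 × 45.1% = 31.6%.

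**4. Non-switchers in the before column.** If half switch, and the others have twice the rate (0.20) over 5 months, their figure is 1 − exp(−1.0) = 63.2%. The before column moves from 42.4% to 0.5 × 42.4% + 0.5 × 63.2% = 52.8%.

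**5. The same data as rates.** Counting time to first event or end of period, expected time at risk per participant is P / rate. Events divided by time is then P / (P / 0.10) = 0.10 per person-month in both periods, a ratio of 1.0 for any period length.

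**The case against.** The strongest reply is that this is one descriptive listing among about ten. No objective, endpoint or hypothesis compares QW with Q2W safety. That stands, and it limits the weight of the point.

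It is also fair that the SAP never states the whole-set denominator. A reader might infer that the plan expressly mixes non-switchers into the table. The documents do not say so: that reading comes from the SAP 6.7 default plus silence, and the words before and after the switch can be taken to presuppose a switcher. SAP 5.2.13 bases percentages for visit-specific analyses on those still present, but it does not clearly cover this table. If only switchers are meant, steps 3 and 4 fall away. Time at risk, priming and returns to QW remain. The floor of 168 days applies only to switchers.

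The priming effect is narrower than a whole-table distortion. CRS has its own row, so it inflates that row, its SOC and any overall total, but not infections or cytopenias. SAP 6.7.1.1 also reports CRS and ICANS by dose number. SAP 6.7.1.1 and 6.7.1.2 plan time to onset and duration for the events of interest, and SAP 6.3.1 mentions exploratory exposure–safety work outside this SAP. These help a reader, but none splits by interval or supplies time at risk.

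A reader might also infer that the trial intends to claim lower toxicity on Q2W. Protocol 4.3 does not support this; its rationale is that lower dose intensity may be enough to keep a response. Nor do the documents support a bias of known sign: the illustrations go both ways, every rate, duration and switching proportion is assumed, and a constant rate is a simplification because CRS clusters early.

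**Conclusion.** The concern holds as a limit on what this table can show. As written, it gives crude percentages over periods of unequal length. The priming doses sit on one side, the population rests on a default, and returns to QW are unassigned. With no interval effect and an assumed 0.10 events per person-month, time at risk alone gives 42% before against 18% to 59% after. Size and direction in the trial itself cannot be known from the documents.

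The change is worth making because a better table can be built from data already derived for exposure. Even then the table would not isolate the effect of the interval. Switchers are selected responders, interval is confounded with time on treatment, and there is no concurrent control. Restricting to switchers also means that nobody in the before column can have had a fatal or permanently discontinuing event.

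**What to change.** In SAP 6.7.1:

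1. Base both columns on participants who switched to Q2W, and state that denominator by cohort and overall.
2. Show the priming period separately. Start the QW period at the first 76 mg dose and end it the day before the first Q2W dose.
3. Run the after period from the first Q2W dose to the earlier of return to QW or end of the on-treatment period.
4. Beside the counts, give participant-months at risk and exposure-adjusted rates (participants with an event per participant-month, with time counted to first event or end of period).
5. Add a footnote that the table is descriptive, that switchers are selected responders, that interval is confounded with time on treatment, and that fatal or permanently discontinuing events cannot occur in the before column.

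The cost is SAP wording and modest programming, with no new data: SAP 6.6.3 already plans to report switches and returns to QW. The table will cover fewer participants and will still not be a causal comparison of QW with Q2W.
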